9.1 LABELING, PACKAGING, STORAGE AND RETURN OF CLINICAL SUPPLIES

9.2 Investigational Product

The investigator shall take responsibility for and shall take all steps to maintain appropriate records and ensure appropriate supply, storage, handling, distribution and usage of investigational product in accordance with the protocol and any applicable laws and regulations.

Clinical Supplies will be provided by Merck as summarized in Table 7.

Table 7 Product Descriptions

Product Name & Potency	Dosage Form
Pembrolizumab 50 mg	Lyophilized Powder for Injection
Pembrolizumab 100 mg/ 4mL	Solution for Injection

Proprietary Information of MD Anderson Document Product: JMK 3479, 2016 Protocol/Amendment No.: NCT02882282

9.3 Packaging and Labeling Information

Clinical supplies will be affixed with a clinical label in accordance with regulatory requirements.

9.4 Clinical Supplies Disclosure

This trial is open-label; therefore, the subject, the trial site personnel, the IND Office and/or designee are not blinded to treatment. Drug identity (name, strength) is included in the label text; random code/disclosure envelopes or lists are not provided.

9.5 Storage and Handling Requirements

Clinical supplies must be stored in a secure, limited-access location under the storage conditions specified on the label.

Receipt and dispensing of trial medication must be recorded by an authorized person at the trial site.

Clinical supplies may not be used for any purpose other than that stated in the protocol.

9.6 Returns and Reconciliation

The investigator is responsible for keeping accurate records of the clinical supplies received from Merck or designee.

Upon completion or termination of the study, all unused and/or partially used investigational product will be destroyed at the site per institutional policy. It is the Investigator's responsibility to arrange for disposal of all empty containers, provided that procedures for proper disposal have been established according to applicable federal, state, local and institutional guidelines and procedures, and provided that appropriate records of disposal are kept.

Document Product: JMK-3475, 2016
Protocol/Amendment No.:

10.1 APPENDICES

10.2 ECOG Performance Status

Grade	Description	
0	Normal activity. Fully active, able to carry on all pre-disease performance without restriction.	
1	Symptoms, but ambulatory. Restricted in physically strenuous activity, but ambulatory and able to carry out work of a light or sedentary nature (e.g., light housework, office work).	
2	In bed <50% of the time. Ambulatory and capable of all self-care, but unable to carry out any work activities. Up and about more than 50% of waking hours.	
3	In bed >50% of the time. Capable of only limited self-care, confined to bed or chair more than 50% of waking hours.	
4	100% bedridden. Completely disabled. Cannot carry on any self-care. Totally confined to bed or chair.	
5	Dead.	

^{*} As published in Am. J. Clin. Oncol.: Oken, M.M., Creech, R.H., Tormey, D.C., Horton, J., Davis, T.E., McFadden, E.T., Carbone, P.P.: Toxicity And Response Criteria Of The Eastern Cooperative Oncology Group. Am J Clin Oncol 5:649-655, 1982. The Eastern Cooperative Oncology Group, Robert Comis M.D., Group Chair.

10.3 Common Terminology Criteria for Adverse Events V4.0 (CTCAE)

The descriptions and grading scales found in the revised NCI Common Terminology Criteria for Adverse Events (CTCAE) version 4.0 will be utilized for adverse event reporting. (http://ctep.cancer.gov/reporting/ctc.html)

10.4 Criteria for evaluating clinical and histologic responses

Definitions of clinical response (to be recorded at months 3 and 12):

- disease progression: increase of at least 25% in the sum of the product of the diameters of all visible lesions compared to baseline, and/or development of new lesions compared to baseline
- partial response: decrease of at least 50% in the sum of the product of the diameters of all visible lesions compared to baseline
- complete response: resolution of all baseline visible lesions
- stable disease: all other cases

Proprietary Information of MD Anderson Document Protect: JMK 2479, 2016 NCT02882282

Definitions of histological response (to be recorded at months 3 and 12):

- yes: resolution of baseline hyperplasia / hyperkeratosis / parakeratosis, resolution of baseline dysplasia, or improvement of baseline dysplasia by at least one grade
- no: all other cases

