5.5.2 Prohibited Concomitant Medications

Subjects are prohibited from receiving the following therapies during the Treatment Phase of this trial:

- Antineoplastic systemic chemotherapy or biological therapy (with the exception of adjuvant hormonal therapy)
- Immunotherapy not specified in this protocol
- Investigational agents with anti-neoplastic activity other than pembrolizumab
- Radiation therapy
- Live vaccines within 30 days prior to the first dose of trial treatment and while participating in the trial. Examples of live vaccines include, but are not limited to, the following: measles, mumps, rubella, varicella/zoster, yellow fever, rabies, BCG, and typhoid vaccine.
- Systemic glucocorticoids for any purpose other than to modulate symptoms from an event of clinical interest of suspected immunologic etiology. The use of physiologic doses of corticosteroids may be approved after consultation with the Principal Investigator.

Subjects who, in the assessment by the investigator, require the use of any of the aforementioned treatments for clinical management should discontinue treatment on trial. Subjects may receive other medications that the investigator deems to be medically necessary.

The Exclusion Criteria describes other medications which are prohibited in this trial.

There are no prohibited therapies during the Post-Treatment Follow-up Phase.

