7.1.1.7 Concomitant Medications Review

Concomitant medications will be documented in the electronic medical record so that the information is available for post-hoc analysis of outcomes related to the study, if relevant. Concomitant medications will not be captured in the electronic trial database.

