7.1.1.8 Oral Cancer-Free Survival Status

Information on time to development of oral cancer/disease progression/recurrence, sites of disease, development of second primary tumors, additional therapy, long-term survival, and other relevant clinical data may be obtained throughout and after the study period as deemed necessary by the Principal Investigator for trial data interpretation. Patients (or their family members or designees) may be contacted by telephone or in writing or by electronic mail or during clinic visits during or after treatment discontinuation for collection of oral cancersurvival status. The information may also be obtained through chart reviews.

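### The response criteria do not say how to score a lesion that is excised or ablated after randomization; read literally, they score it as a response, mainly at month 12

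*Combined protocol and SAP*

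**What the plan says.** Section 10.4 defines three ways to be a responder, all relative to baseline:

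- Clinical, complete: "complete response: resolution of all baseline visible lesions".
- Clinical, partial: "partial response: decrease of at least 50% in the sum of the product of the diameters of all visible lesions compared to baseline".
- Histologic: "yes: resolution of baseline hyperplasia / hyperkeratosis / parakeratosis, resolution of baseline dysplasia, or improvement of baseline dysplasia by at least one grade".

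Both kinds of response are "to be recorded at months 3 and 12". New lesions, or growth of at least 25%, count as progression. No definition mentions lesions removed by surgery, laser or other local treatment.

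Section 5.5.2 opens its list with "Subjects are prohibited from receiving the following therapies during the Treatment Phase of this trial". The list covers systemic anti-neoplastic and biological therapy, other immunotherapy, investigational agents, radiation, live vaccines and systemic glucocorticoids. It does not name excision or ablation. The section then states: "There are no prohibited therapies during the Post-Treatment Follow-up Phase".

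On data capture, 7.1.1.7 says "Concomitant medications will not be captured in the electronic trial database", although medications are documented in the medical record. Section 7.1.1.8 says that "additional therapy, long-term survival, and other relevant clinical data may be obtained" as the Principal Investigator judges necessary.

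Section 8.3 analyses patients as randomized. It gives no rule for response after local treatment of a lesion.

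**The concern.** Objective 3 (section 3.3) asks whether pembrolizumab reverses histologic change and shrinks visible lesions. Section 4.2.3.1 adds that response will be related to long-term oral cancer-free survival. Both uses need a responder to be someone whose lesion regressed.

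The protocol expects some lesions to worsen. Section 5.8.1 lists worsening oral lesions as a reason to stop therapy and asks that patients who stop early stay on study and continue assessments where possible. If such a lesion is then cut out or ablated, the patient can reach month 12 with nothing visible. The written rule would score that as a response. The stated response rate would then mix regression with removal, and some patients whose lesions did badly would sit in the responder group when response is set against cancer-free survival. Because additional therapy need not be recorded, the analysis dataset may not show which patients these are.

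**Working it through.** The documents state no response rate, excision rate or power for response, so there is no figure to reproduce. The check is a reading of the rules, followed by an illustration of size.

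**Step 1: partial response.** Let S0 be the baseline sum of products and R the part contributed by lesions later removed. A removed lesion has product 0. If the remaining lesions are unchanged and none is new, the sum becomes S0 − R. The rule is met when R is at least 0.5 × S0. It is always met when the removed lesion was the only one. This criterion is purely dimensional, so it does not depend on what *resolution* is taken to mean.

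**Step 2: complete response.** If all baseline lesions are removed, none remains visible. Read literally, the complete-response rule is met.

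**Step 3: histologic response.** A yes needs later tissue showing resolution or a lower grade. Section 7.1.5 schedules biopsies at baseline and at months 3 and 12. If the month-12 sample after removal is clear or of lower grade, the patient scores yes. If there is no sample, the patient might fall under the residual no category or be missing; the text does not settle which.

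**Step 4: opportunity.** From month 3 to month 12 nothing is prohibited (5.5.2), so the month-12 assessment is the more exposed. For month 3 the gap is that the treatment-phase list omits excision and ablation. Section 5.2.1.2 also allows dosing to be interrupted for surgical events, with no matching scoring rule.

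**Step 5: size (all rates assumed).** Let p be the true response rate, and e the share of true non-responders whose lesions are removed before assessment and who then score as responders. True responders stay responders under the literal rule, so

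observed rate = p + (1 − p) × e.

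With p = 20%:

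- e = 5%: 0.20 + 0.80 × 0.05 = 24%
- e = 10%: 0.20 + 0.80 × 0.10 = 28%
- e = 20%: 0.20 + 0.80 × 0.20 = 36%
- e = 30%: 0.20 + 0.80 × 0.30 = 44%

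Over the same range of e, p = 10% gives 14.5% to 37%, and p = 30% gives 33.5% to 51%.

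**The case against.** The best reply is that the protocol nowhere says an excised lesion counts as a response. Objective 3 speaks of response to pembrolizumab, and 7.1.4.1 and 7.1.5 speak of response to treatment. A sensible assessor could read *resolution* as excluding surgical removal. That is fair: the documents are silent, and it would be wrong to say they intend to count removals. But the reading does not rescue the partial-response rule, which is arithmetic on diameters. It also leaves each assessor to supply an unwritten exception in an open-label trial.

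A second reply is that this is a single-institution trial with lesion measurements in the chart, and 7.1.1.8 permits chart review. Removals done there may well be traceable. The sentence in 7.1.1.7 concerns medications rather than procedures, and so is weak evidence here. This stands, but finding a removal afterwards does not supply a rule for scoring it.

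Several stronger readings are tempting, and the documents do not support them:

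- **The worst lesions become responders.** Only in part. Under 5.8.1, patients who develop oral cancer have only the long-term follow-up procedures, so no month-12 lesion measurement or biopsy is scheduled for them. New lesions are progression under 10.4.
- **The difference between arms is pulled toward zero or reversed.** No excision rate is given for either arm, so the direction is unknown. Section 8.3 names no between-arm test of response.
- **Counts of affected patients out of 52 per arm (104 / 2).** Clinical response applies to the measurable-lesion subgroup (3.3), and a visible lesion is not required for entry (5.1.1). The subgroup's size is not stated.
- **The main result is affected.** The response criteria do not enter the primary endpoint definition or the sample size.

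**Conclusion.** The concern holds as a missing scoring rule for a foreseeable event after randomization. Taken literally, 10.4 classifies a patient whose lesion was removed as at least a partial responder once the removed part makes up half the baseline sum and there is no new or offsetting growth. It classifies that patient as a complete responder if all baseline lesions are gone. A histologic yes follows only if later tissue supports it.

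The effect is confined to secondary endpoints, mainly at month 12. It can inflate the response rates of Objective 3 and distort the planned association between response and oral cancer-free survival. Its size cannot be derived from the documents. The range of 24% to 44% for a true 20% rests on assumed values of p and e, and on every such removal being scored as a response. The point deserves correction before response is assessed, but it does not threaten the primary analysis.

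**What to change.** Add to 10.4: a patient with any baseline lesion excised, ablated or otherwise locally treated after randomization (incisional study biopsies excepted), or given other anti-neoplastic therapy, is scored a non-responder, clinically and histologically, at every later assessment. Add a sensitivity analysis that uses the last assessment before the intervention. Record the date and type of each such intervention in the trial database, for both arms, at visits already scheduled, and report the frequency by arm.

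The cost is a few sentences in 10.4, a short case-report entry and one extra analysis, with no new visits or procedures. The rule governs scoring only and does not change how any patient is treated.

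The downside is a somewhat lower month-12 rate, because a true month-3 responder whose residual lesion is later removed becomes a non-responder. If f is the share of true responders affected, the rate becomes p × (1 − f). With p = 20% and assumed f of 5%, 10% and 30%, this gives 19%, 18% and 14%. The loss is therefore slight if such removals are uncommon, and the sensitivity analysis would show it. Scoring these patients as not evaluable is an alternative; whichever rule is chosen should be written down in advance.

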3.3 Secondary Objective(s) & Hypothesis(es)

(2) **Objective**: To determine safety and tolerability of pembrolizumab for patients with oral IEN

Hypothesis: Pembrolizumab will have similar or better toxicity profile as in patients with advanced cancers

(3) **Objective**: To determine the histologic and clinical response rates (in the subgroup of patients with clinically evident, measurable oral IEN lesions) to pembrolizumab

Hypothesis: Pembrolizumab will reverse histologic changes associated with oral IEN, and will reduce the size of clinically evident oral IEN lesions (i.e., leukoplakia and/or erythroplakia)

(4) **Objective**: To characterize the immune infiltrate in oral IEN lesions before and after treatment with pembrolizumab.

Hypothesis: Pembrolizumab will stimulate a specific, monoclonal / oligoclonal adaptive immune response

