5.1 METHODOLOGY

5.2 Entry Criteria

5.1.1 Diagnosis/Condition for Entry into the Trial

Histological evidence of oral intra-epithelial neoplasia within 12 months prior to enrollment. Subjects with a history or clinical diagnosis suggestive of oral intra-epithelial neoplasia, or patients with a history of invasive oral cancer are eligible, but must have a confirmed histological diagnosis of oral intra-epithelial neoplasia before randomization. Histological evidence of oral intraepithelial neoplasia on an invasive oral cancer resection specimen is acceptable.

A visible, measurable, clinical lesion (such as leukoplakia and/or erythroplakia) is not required.

Loss of heterozygosity (LOH) profiles will be determined in the oral intra-epithelial neoplasia lesion in a CLIA-certified lab, and 2described in sections 5.1.2 and 5.1.3. High risk LOH profiles (i.e., LOH positive cases) are defined as follows:

Patients without a prior oral cancer history: LOH at 3p14 and/or 9p21 plus at least at one additional chromosomal site (4q, 8p, 11p, 13q, or 17p)

Patients with a prior oral cancer history: LOH at 3p14 and/or 9p21

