5.8.1 Discontinuation of Study Therapy

Subjects must discontinue therapy for the following reasons:

- Withdrawal / discontinuation from study.
- Worsening oral lesions requiring discontinuation from study therapy, in the opinion of the treating physician
- Unacceptable adverse experiences as described in Section 5.2.1.2
- Intercurrent illness that prevents further administration of treatment
- Investigator's or patient's decision
- The subject has a confirmed positive serum pregnancy test
- Development of oral cancer
- The subject is lost to follow-up

For patients that develop oral cancer during the study or for patients that are lost to follow up, only the procedures described under "Lon-Term Follow-Up" in section 6.0 will be performed.

If possible, subjects that discontinue therapy before completing 4 cycles of treatment should remain on study and continue to undergo study procedures and follow-ups as described in Section 6.0.

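### The clinical response rule does not name invasive cancer as progression and makes stable disease a catch-all, so a biopsy-proven cancer can be graded stable

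*Combined protocol and SAP*

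**What the plan says.** Section 10.4 sets four clinical categories, to be recorded at months 3 and 12. The size limb of progression is "disease progression: increase of at least 25% in the sum of the product of the diameters of all visible lesions compared to baseline". A new lesion since the baseline visit is enough on its own to count as progression too. Partial response is a fall of at least 50% in the same sum. The third category is "complete response: resolution of all baseline visible lesions". Whatever is left over falls into the last one: "stable disease: all other cases". Invasive cancer appears in none of them, there is no not-evaluable category, and stable disease does not require a measurement.

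The flow chart (6.2) schedules oral lesion measurement and new tissue collection at the same post-baseline visits, with no footnote limiting measurement to the experimental arm. Section 7.1.5 explains that biopsies at baseline, month 3 and month 12 watch for histological progression and invasive cancer.

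Section 5.8.1 narrows what is done later: "For patients that develop oral cancer during the study or for patients that are lost to follow up, only the procedures described under". The flow-chart column it points to is the one for long-term follow-up, which does not include lesion measurement.

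Clinical response is a secondary objective (3.3), assessed "in the subgroup of patients with clinically evident, measurable oral IEN lesions". Section 5.1.1 adds: "A visible, measurable, clinical lesion (such as leukoplakia and/or erythroplakia) is not required". Histologically confirmed oral cancer is a primary-endpoint event (8.3).

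**The concern.** The trial exists to prevent invasive oral cancer, yet a lesion that has become cancer can receive a grade that reads as disease control, or even as response. The histologic rule in 10.4 defaults safely, because its leftover cases count as no response. The clinical rule defaults to stable.

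Two things are at stake. First, the progression and stable percentages reported for the secondary objective would be wrong for these patients, and two analysts could tabulate the unmeasured patients differently. Second, section 4.2.3.1 keeps response as a secondary endpoint partly to study its association with long-term oral cancer-free survival. Grading patients who have already had the primary event as stable blurs that association, whatever the treatment effect.

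**Working it through.** **Step 1. A cancer found at a visit where the lesion is measured.** Suppose the month-3 biopsy shows invasion in a lesion whose area grew 10%, with no new lesion. The size part of progression fails (10% < 25%) and so does the new-lesion part. Partial and complete response fail too. What remains is stable disease. If the same lesion had shrunk by half, the grade would be partial response. This case does not depend on 5.8.1, since measurement and biopsy belong to the same visit.

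**Step 2. A patient with no measurement.** Suppose cancer is diagnosed at month 6. Under 5.8.1 and the flow chart no month-12 measurement is scheduled. Progression by size, partial response and complete response cannot be assessed. The residual class could be applied, or the patient could be treated as missing. Neither 10.4 nor 8.3 says which. Death or loss before the visit raises the same question.

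**Step 3. The plan's own rates.** The documents give no figure for clinical response, so I use the cancer hazards in the sample size justification (8.2). They follow from the stated two-year rates:
- prior cancer, control: -ln(1 - 0.21)/2 = 0.1179
- no prior cancer, control: -ln(1 - 0.15)/2 = 0.0813
- treated, at hazard ratio 0.45: 0.45 × 0.1179 = 0.053 and 0.45 × 0.0813 = 0.0366

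All four match the plan. A 10,000-run simulation with these hazards, uniform accrual, 10% uniform loss and the stated boundaries gives 78.4% power against the stated 79%. At hazard ratio 0.4 it gives 85.5% against 88%, a gap that depends on my accrual and loss assumptions and has no bearing here.

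**Step 4. Ceiling on affected patients.** The 56 and 48 patients split 1:1 give 28 and 24 per arm. Expected cancers per arm by t years = 28(1 - exp(-λ1 t)) + 24(1 - exp(-λ2 t)).

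| By | Control, of 52 | Pembrolizumab, of 52 |
|---|---|---|
| Month 3 (t = 0.25) | 1.3 (2.5%) | 0.6 (1.1%) |
| Month 12 (t = 1) | 3.11 + 1.87 = 5.0 (9.6%) | 1.45 + 0.86 = 2.3 (4.4%) |

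This is a ceiling. It treats all 52 as having a measurable lesion, supposes that no cancer already shows 25% growth or a new lesion, and supposes that every unmeasured cancer case is called stable.

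**Step 5. Measurable-lesion subgroup.** Its size is not in the documents. If 25% to 75% have such a lesion (assumption), month 12 gives 0.25 × 4.99 = 1.2 to 0.75 × 4.99 = 3.7 control patients, and 0.25 × 2.31 = 0.6 to 0.75 × 2.31 = 1.7 on pembrolizumab. As a share of the subgroup the ceiling stays at 9.6% and 4.4% if its cancer rates are the same (assumption). Cancers already caught by the size or new-lesion rule lower all of these.

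**Step 6. Other unmeasured patients.** The plan assumes 10% loss, uniform in time. Spread over 3 to 7 years (assumed window), loss by month 12 is 10%/7 = 1.4% to 10%/3 = 3.3%, or 0.7 to 1.7 of 52 per arm.

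**The case against.** The strongest reply is that clinical response is meant as a visual measure and cancer is captured elsewhere: as the primary event, through the biopsies, and in the histologic response rule. On this view, keeping size separate from histology is what allows its association with cancer-free survival to be studied, and making cancer override size builds the primary event into the response variable. That caution stands and shapes the fix. It does not rescue a category called stable disease that includes proven invasion.

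A reader might infer that every patient who develops cancer, dies or is lost will be tabulated as stable. The documents do not support that. Growth of 25% or a new lesion is already progression, and a patient with no scheduled measurement is as naturally missing as stable. For these patients the defect is the absence of a rule.

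A reader might also infer a bias against the drug, up to 9.6% - 4.4% = 5.2 points in the progression contrast. That depends on the assumed hazard ratio of 0.45; with no effect the counts are 5.0 and 5.0. Objective 3 concerns response to pembrolizumab, and 8.3 specifies no between-arm test of clinical response and no progression or stable-disease rate.

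Finally, a lesion excised with its cancer could literally satisfy the complete response wording. But 5.8.1 leaves no scheduled measurement after cancer, so the documents do not show that it would be recorded.

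**Conclusion.** The point holds in limited form. For a lesion measured at the visit, 10.4 as written can put biopsy-proven invasive cancer under stable disease or partial response; this is a stated rule giving a wrong category. For unmeasured patients the plan is silent.

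The size is a handful of patients at most, within the ceilings in steps 4 and 5. Those rest on the plan's hazards, even allocation within strata, and an assumed subgroup share with the same cancer rates. The effect is confined to a secondary, descriptive endpoint: mainly the progression and stable percentages, and the response rate only where an invasive lesion has halved. The primary analysis and its power do not change. The correction is worth making because it is cheap and removes an ambiguity before any table is produced.

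**What to change.** In 10.4:
- (a) Add histologically confirmed invasive oral cancer at or before the assessment to disease progression, overriding the size-based categories.
- (b) Restrict stable disease to lesions measured at the visit that meet none of the other definitions.
- (c) Report other unmeasured patients (death, loss, refusal) separately as not evaluable, and state whether they stay in the denominator of the response rate, which is a matter of convention.
- (d) Make 10.4 consistent with 5.8.1 by saying how patients moved to long-term follow-up only are classified at months 3 and 12.

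This needs no new visits or data, because cancer dates are already collected for the primary endpoint. There are two costs. The stable-disease percentage becomes slightly less favourable. And because progression would then contain the primary event, any association between clinical response and oral cancer-free survival should also be shown with the size criteria alone.
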